8.1 Specification of Safety Parameters

Safety Assessment: DaTSCAN is a commercially approved tracer so this study is not designed to specifically evaluate safety. However, subjects will be asked if they experienced any unusual effects during the study and the debriefing period. Any adverse events will be recorded in the subject's data, either in the case report form or on the serious adverse events form.

Safety Evaluation: Adverse events will be recorded in the subject's data. Additional side effects and symptoms will be recorded in each subject's case report forms. This data will be pooled at the conclusion of the study in order to assess any additional safety concerns with the radiopharmaceutical or the imaging procedure. It should be noted that any study participant who experiences a serious adverse event directly related to the DaTSCAN will be excluded from further study using this radiopharmaceutical. For the purposes of this study, any adverse events or serious adverse events occurring within the duration of the study procedures that include the administration of DaTSCAN and the SPECT scan will be recorded and reported as indicated by regulation and IRB policy. However, events occurring after the SPECT scan dates and prior to the follow up scan dates will not be considered adverse events for the purposes of this study.

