8.2 Methods and Timing for Evaluating Safety

Since all safety monitoring of DaTSCAN will be performed on the day of the scan, safety information will be available on an immediate basis. Should a significant subject reaction occur during the administration of the DaTSCAN, no additional studies will be performed until the specific batch of DaTSCAN can be fully analyzed and tested for purity, pyrogenicity, and sterility by GE Medical. If it is determined that there was not a problem with the DaTSCAN product, the subject will be withdrawn from the study and additional subjects may be injected and scanned with DaTSCAN. If however, there is a problem with the batch of DaTSCAN, no studies will be performed until the problem with the batch can be evaluated and corrected in future batches.

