8.3 Procedures for Eliciting Reports and Reporting Adverse Events

Subjects will be evaluated during the injection period, immediately post injection, and prior to leaving on the day of imaging with a brief examination of the injection site and with a clinical evaluation to determine if the subject had any unusual experiences during the injection or scanning procedure. Subjects will be contacted by phone approximately one week after the scanning in order to assess for any further adverse events. For the purposes of this study, any adverse events or serious adverse events occurring on the day of administration of DaTSCAN and scan will be recorded and reported as indicated by regulation and IRB policy. After the imaging day , the subject will be considered to have completed the study and will not longer be followed.

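### Sections 8.1 to 8.3 give conflicting adverse-event windows: a call looks for late events, but related events starting between the two scans are not classed as adverse events

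*Combined protocol and SAP*

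**What the plan says.** Each subject has two DaTSCAN injections, one before the retreat and one after it (2.4, 4.2). The safety text then sets these rules:

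- **8.3, the call.** "Subjects will be contacted by phone approximately one week after the scanning in order to assess for any further adverse events". The text does not say whether this follows the first scan, the second, or both.
- **8.3, recording.** The same paragraph says that "any adverse events or serious adverse events occurring on the day of administration of DaTSCAN and scan will be recorded and reported".
- **8.3, end of follow-up.** After the imaging day, "the subject will be considered to have completed the study and will not longer be followed".
- **8.2.** The stated premise is that "all safety monitoring of DaTSCAN will be performed on the day of the scan".
- **8.1, exclusion.** "events occurring after the SPECT scan dates and prior to the follow up scan dates will not be considered adverse events". No exception is made for events that are related or serious.
- **8.1, statements without a time window.** "Any adverse events will be recorded in the subject's data", and "Additional side effects and symptoms will be recorded" in the case report forms. The data are pooled at study end to look for safety concerns with the tracer or the imaging procedure.

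Elsewhere, 8.4 and 4.6 provide six-month follow-up after certain adverse events. Section 5.3 ties some withdrawal follow-up and a recruitment hold to adverse or serious adverse events, and 9.7 puts all subjects in a safety analysis.

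**The concern.** A call made to find further adverse events has a purpose only if an event found that way can count as one. Under 8.3's own recording sentence, an event that starts after the scan day falls outside what will be recorded and reported. Under 8.1, an event that starts between the scans is not an adverse event at all. The likely aim of the 8.1 sentence is to keep retreat-period events from being attributed to the tracer, but as written it also removes delayed events that are related to the study procedures.

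What is at stake is classification. The label decides what appears as an adverse event in the pooled safety data, and it is the condition for rules such as the 8.4 follow-up of events directly related to DaTSCAN. The affected interval is the one in which the subject is still due a second injection. Two sites, or two coordinators, could handle the same complaint differently and each point to a sentence that supports them.

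**Working it through.** No figure in the plan bears on this point, so the check is a comparison of the rules by date of onset.

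**Step 1: the calendar.** Under 4.2, scan 1 falls within the month before the retreat and scan 2 within a week after it ends. Retreat length is not given. A call about seven days after scan 1 would therefore normally fall between the scans. If the interval were shorter than a week, only the days before scan 2 would be covered by the 8.1 exclusion.

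**Step 2: apply each rule by onset.**

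| Onset of event | 8.1 between-scan exclusion | 8.3 scan-day recording | Result |
|---|---|---|---|
| Scan day 1, even if first reported at a call | does not apply | inside | adverse event |
| After scan day 1, before scan 2 | applies | outside | not an adverse event |
| Scan day 2, even if first reported at a call | does not apply | inside | adverse event |
| After scan day 2 | does not apply | outside | unclear: not excluded, but no commitment to record |

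The last row is unclear because 8.4 and 5.3.c refer to related events without any onset window, while 8.3 limits recording to the scan day.

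**Step 3: apply the two readings of the call.**

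- *The call follows scan 1 (alone or as well as scan 2).* Anything found at the call after scan 1 with onset after the scan day is in row 2. That call can yield an adverse event only from row 1.
- *The call follows scan 2 only.* It does not meet the 8.1 exclusion. It still conflicts with 8.3's own recording limit and end of follow-up (row 4), and 8.1 still removes row 2 events from the class.

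On both readings, row 2 stands and 8.3 is at odds with itself.

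**Step 4: what happens to a row 2 complaint.** The statements without a time window in 8.1, and the subject reports mentioned in 4.9, may place it in the case report form. Because side effects and symptoms are pooled with the rest, it may also reach the end-of-study safety data, though not as an adverse event. The 8.4 follow-up starts from an adverse event directly related to DaTSCAN, so it is not clearly triggered. Section 5.3.a is different: it stops further DaTSCAN scans for the reactions it names, whatever they are called.

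**Step 5: the follow-up statements.** Section 8.3 ends follow-up after the imaging day. This does not sit with its own call, with a second scan still to come after scan 1, or with the six-month follow-up in 4.6 and 8.4. Those two also count the six months from different points: the adverse event in 4.6, the injection in 8.4.

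**The case against.** The strongest reply is that this is an approved tracer and, in the protocol's words, "this study is not designed to specifically evaluate safety". Limiting adverse events to scan days is a defensible choice that avoids attributing retreat events to the tracer. The call may serve only to pick up scan-day events reported late. It may also follow only the last scan: 8.3's remark about having completed the study fits the final imaging day better, since nobody has completed the study after scan 1.

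Much of this stands. The text does not establish that the call follows scan 1, and late reporting of scan-day events is a proper use of it. But 8.3 states the purpose as further adverse events, without that limit. Reading the call as a late-report check would remove the contradiction and still leave delayed related events unclassified.

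Three stronger readings are tempting, and the documents do not support them.

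- *Delayed events vanish from the safety data.* Side effects and symptoms are recorded without a time window and pooled, so a complaint may appear there under another label.
- *Every rule tied to adverse events fails for the procedural risks the protocol names.* Phlebitis and infection are listed in 2.3 as cannulation risks and described as very remote. The 8.4 follow-up needs an event directly related to DaTSCAN. The 8.1 exclusion from further tracer study needs a serious event directly related to DaTSCAN, and the 5.3.c hold needs a serious one directly related to DaTSCAN or the fMRI scan. A cannulation event would not clearly meet those terms even if it were classed as an adverse event.
- *A subject who reacts would be injected again.* Section 5.3.a stops further scans for its named reactions regardless of label.

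**Conclusion.** The inconsistency is real and is in the current text. Sections 8.1, 8.2 and 8.3 do not give one adverse-event window, and 8.1 taken literally declassifies delayed related events that start between the scans. That conclusion does not depend on which scan the call follows. The sharper statement, that a call after scan 1 can yield no adverse event except one that began on the scan day, assumes that there is such a call and that it falls before scan 2.

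The size is minor to moderate. Every subject who has the first injection passes through the affected interval. How many would have a delayed related event cannot be estimated, because the documents give no rate. The effect is on the adverse-event label and the rules that depend on it. The study is not built to evaluate safety, and no imaging conclusion changes.

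**What to change.** 1. In 8.1 and 8.3, state one adverse-event recording window that runs through the call already planned, with onset date and relatedness recorded for each event.
2. In 8.3, say which scan or scans the call follows.
3. In 8.1, limit the between-scan exclusion so that it does not remove events reported at that call. It may still cover later retreat-period events.
4. Reconcile 4.6, 5.3, 8.1, 8.2, 8.3 and 8.4 on which events count and how long subjects are followed, including 8.3's statement that follow-up ends after the imaging day. This asks for consistent wording; it does not propose a new follow-up, withdrawal or stopping rule.

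The cost is a set of text edits. If the call is meant to follow one scan only, and the sponsor chooses to have it follow both, there is one extra call per subject. A few more minor events will be recorded, some of them due to the retreat, and each will need a judgement of relatedness.

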8.2 Methods and Timing for Evaluating Safety

Since all safety monitoring of DaTSCAN will be performed on the day of the scan, safety information will be available on an immediate basis. Should a significant subject reaction occur during the administration of the DaTSCAN, no additional studies will be performed until the specific batch of DaTSCAN can be fully analyzed and tested for purity, pyrogenicity, and sterility by GE Medical. If it is determined that there was not a problem with the DaTSCAN product, the subject will be withdrawn from the study and additional subjects may be injected and scanned with DaTSCAN. If however, there is a problem with the batch of DaTSCAN, no studies will be performed until the problem with the batch can be evaluated and corrected in future batches.

8.3 Procedures for Eliciting Reports and Reporting Adverse Events

Subjects will be evaluated during the injection period, immediately post injection, and prior to leaving on the day of imaging with a brief examination of the injection site and with a clinical evaluation to determine if the subject had any unusual experiences during the injection or scanning procedure. Subjects will be contacted by phone approximately one week after the scanning in order to assess for any further adverse events. For the purposes of this study, any adverse events or serious adverse events occurring on the day of administration of DaTSCAN and scan will be recorded and reported as indicated by regulation and IRB policy. After the imaging day , the subject will be considered to have completed the study and will not longer be followed.

8.4 Type and Duration of Follow-up of Subjects After Adverse Events

Subjects will be followed six months after the injection if they experienced an adverse event directly related DaTSCAN. If there is no further problem, this will terminate the follow up. However, if the subject continues to have problems directly related to the DaTSCAN, then they will continue to be followed at six months intervals until the adverse event resolves or until the subject's death.

9. Statistics

9.1 Description of Statistical Methods Region of Interest Analysis.

The images of each of the scans will be reconstructed and resliced, using an oblique reformatting program, according to the anterior-posterior commissure line. The SPECT images will be co-registered with the anatomical MRI and comparable slices of the cerebral cortex will be examined. A previously validated template methodology consisting of regions of interest (ROI) corresponding to the major cortical and subcortical structures will be placed over the scans (Resnick 1993). For the purposes of this study, we will examine the regional CBF, serotonin transporter and dopamine transporter activity in only a selected number of ROIs which will be hypothesis driven. The ROIs to be examined based on the hypotheses described above and the preliminary findings will be the inferior frontal, superior frontal, dorsolateral prefrontal, orbitofrontal, dorsal medial cortex, inferior temporal, amygdala, hippocampus, superior parietal, inferior parietal, occipital, and sensorimotor areas, as well as the caudate, putamen, thalami, midbrain, hypothalamus, cerebellum, and cingulate gyrus regions. Each ROI will have its placement adjusted manually in order to achieve the best fit according to the atlas. The ROIs will then be copied directly onto each of the scans. This will be possible because the images will

already resliced into the same planes as described above. Counts will be obtained for each ROI and normalized to the mean whole brain counts. This will result in ratios of activity in each ROI will be compared across scans for each neuropsychological state. Other covariables such as age, and psychological measures, can also be included in the statistical analysis. The cerebral structures will be identified by their Talairach coordinates (Talairach 1988).

Statistical parametric mapping (SPM):

The traditional method for analyzing brain fMRI and SPECT images involves the ROI method described above. However, it has long been known that ROI definition, particularly on functional images, is time-consuming, subjective and prone to operator bias. Small regular ROI's are capable of resolving localized focal changes between images, although they are subject to a loss of specificity due to the problems associated with multiple comparisons. Alternatively, large ROI's encompassing an entire brain structure may dilute small activation foci, with a subsequent loss of sensitivity. Unless a study is very strongly hypothesis driven, and comparisons between images are only being made in highly specific regions, ROI analysis lacks the power to accurately distinguish regional variations between a set of images. The solution to this problem has been the development of pixel-based statistical analyses, where the regions are effectively reduced to single pixels (Acton 1998). This method can also be utilized to observe changes in structures not included as part of the ROI analysis.

Therefore, SPM2 software (Wellcome Department of Cognitive Neurology, London, UK) will also be performed in which the image volumes of transverse slices will be made compatible with SPM by creation of usable headers for the images. To begin, a file will be created for each image that contains data on image size, number of slices, pixel depth, maximal pixel value, and voxel size. SPM analysis then requires 1) spatial normalization of all images into the same stereotactic space, 2) smoothing, and 3) statistical parametric comparisons. Spatial Normalization will begin by having the scans from each individual subject will be coregistered to each other, using a rigid-body transformation. To correct for global brain shape differences, the individual MRI volume acquisitions will be transformed into a standard 3D space (MNI, provided by SPM). The images will be coregistered to a MNI atlas template, using affine transformations and nonlinear warping ($7 \times 8 \times 7$ basis functions). The resulting spatially normalized images had isotropic voxels of size 2 mm. The normalized images will be smoothed by convolving with an isotropic FWHM 12 mm Gaussian kernel that allows the subsequent voxel-by-voxel analysis. This reduces the effects of image noise and conditions the data for subsequent statistical tests performed in SPM.

Groups of images will be compared voxel-by-voxel using SPM (Friston 1995). Statistically significant differences between sets of data will be assessed at each voxel with a threshold of P < 0.001. To correct for correlated multiple comparisons, clusters of voxels which survive this threshold will be assessed further using the theory of random Gaussian fields (Friston 1994, 1995b; Worsley 1994), which calculates the significance of clusters based on their peak height and spatial extent. With this technique, differences in blood flow between and within groups will be assessed, and statistic images generated showing significant regional differences between groups. The meditation or activation state can be modeled by a simple one-way analysis of covariance (ANCOVA) with a group effect (the activation) combined with a nuisance or confounding effect (global or reference region activity) to produce the observed data. Other covariables such as age, and psychological measures, can also be included in the statistical

analysis. The cerebral structures will be identified by their Talairach coordinates (Talairach 1988).

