Our preliminary study of cerebral blood flow utilizing SPECT imaging during Tibetan Buddhist meditation demonstrated a number of complex changes including relatively increased cerebral blood flow (CBF) in the prefrontal cortex, the orbitofrontal cortex, and cingulate gyrus, and relatively decreased CBF in the superior parietal region. The results from this study supported the basic hypotheses in this proposal in that there was increased activity in the structures underlying attention and memory processes (Frith 1991). Furthermore, a study by Lazar et al (2005) demonstrated that experienced practitioners of Insight meditation demonstrated increased cortical thickness in the prefrontal cortex when compared to controls. One potential implication is that meditation practice induces long term changes in the brain, but this has not been widely studied on a functional level. Furthermore, functional changes in metabolism and neurotransmitters should theoretically precede structural changes.

The above described functional imaging studies of meditation suggest that there is a network associated with such practices that includes changes in the attentional system of the brain including the prefrontal cortex, cingulate gyrus, and superior parietal lobes. There also appears to be changes of activity in the limbic areas such as the amygdala, hippocampus, and thalamus. An analysis of functional changes will have implications for understanding complex

neurocognitive and affective tasks. Such findings can also assist toward focusing future clinical studies of meditation techniques on specific disorders known to be associated with the same nervous system structures.

We have chosen fMRI imaging of cerebral blood flow for several reasons. We have increasingly utilized fMRI in our studies and fMRI can provide multiple scans on subjects in the same session. This allows for the ability to compare meditation to baseline as well as to other control conditions.

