2.7 References

Please see end of protocol for references.

3. Trial Objectives and Purpose

1. To determine if various neuropsychological states related to a meditation retreat program are associated with changes in the serotonin and dopaminergic systems.

- 2. To determine if there will also be changes in cerebral blood flow using fMRI of that are associated with the dopamine and serotonin transporter activity.
- 3. To analyze and compare pre and post imaging and neuropsychological changes in healthy controls who participate in a meditation retreat program.

4. Trial Design

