b) DaTSCAN SPECT ACQUISITION, PROCESSING, AND ANALYSIS – Subjects will be asked to arrive at the Nuclear Medicine SPECT Center in the morning. A signed consent form will be documented after all questions have been answered. Women of child-bearing potential *must* have a negative pregnancy test within 48 hours *before* proceeding with the SPECT study. Subjects will be given 16 drops of concentrated Lugol's solution in order to block the thyroid. An intravenous catheter will be inserted and capped. Subjects will spend 20 minutes lying supine on an examination table before the radiopharmaceutical is administered to allow them to recover 'physiologically' from the stress of the catheter insertion. 111 to 185 MBq (3 to 5 mCi)¹²³I DaTSCAN will then be administered intravenously. After injection of the ¹²³I DaTSCAN, the subject will have the intravenous catheter removed. They will be able to take a break for lunch. Subjects will then return to the nuclear medicine imaging room 3 hours after ¹²³I DaTSCAN administration for a 60 minute brain scan. The reason for this delay is that kinetic modeling data performed on ¹²³I DaTSCAN has demonstrated that estimation of the binding potential can be made without arterial sampling at this time period (Acton 1998). The subject can be moved from the imaging table after the SPECT study is completed.

All SPECT images may be coregistered with the corresponding anatomic MRI and a previously described template (Resnick 1993), focusing on selected ROIs, will be fit on each

MRI and copied onto the DaTSCAN SPECT images. These ROIs will include the basal ganglia, amygdala and hippocampus, thalamus, brain stem, and cerebellum. To reduce the effects of volume averaging in the axial direction, ROIs will not be placed on the slices that contain the upper most and lower most portions of the structures they represent. This will tend to limit the small ROIs to the central aspect of structures they represent. The primary outcome measure will be the SERT and DAT binding ratios in which the ROI is compared to a reference region (cerebellum) at 4 to 5 hours post administration, when the distribution of ¹²³I DaTSCAN has approached a transient, near equilibrium-like state that reflects the k3/k4 ratio and is related to the binding potential. This allows for a quantitative assessment of SERT binding as described in the Preliminary Studies section.

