The reference region has typically been the cerebellum because this region has such low activity on ¹²³I DaTSCAN scans and no appreciable DAT or SERT receptors. However, values will be obtained for both whole brain regions above the basal ganglia and cerebellar regions in order to confirm the findings. The procedures will be implemented with a commercial statistical package (StatS, Think Point Software, Inc). The reliability of SPM will be evaluated similarly by having two different technicians run the analyses independently. We have found the reliability of the image analysis techniques to be high with intra-class correlations consistently above 0.95.

c) MR image acquisition: Subjects will be studied to evaluate the effects of the meditation retreat program on cerebral activity using fMRI. This approach will enable us to track changes and activation in cerebral activity that result from the program. This data will be correlated to standardized neuropsychological and behavioral measures of cognition, mood, and spirituality.

The fMRI images will be co-registered and comparable slices of the cerebral cortex will be examined pre and post program. We will evaluate changes in baseline brain function while the subject is at rest as well as during the meditation practice itself. Two different analysis approaches will be used since they can provide different types of information. A region of interest analysis will be performed to assess changes of activity in specific brain regions. A comparison between meditation and baseline cerebral activity will indicate which regions of the brain are activated at various stages of meditation.

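### The region-of-interest analysis in section 9.1 divides SERT and DAT counts by a whole-brain mean, but section 4.2(b) defines the primary outcome as the ratio to cerebellum

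*Combined protocol and SAP*

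**What the plan says.** Section 4.2(b), on SPECT acquisition and analysis, is the only place that names a primary outcome measure: "The primary outcome measure will be the SERT and DAT binding ratios in which the ROI is compared to a reference region (cerebellum". It relates this ratio to the binding potential and justifies the cerebellum by its low activity and lack of appreciable DAT or SERT. It then adds a second set of values: "values will be obtained for both whole brain regions above the basal ganglia and cerebellar regions in order to confirm the findings".

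The ROI paragraph of section 9.1 sets its scope in these words: "we will examine the regional CBF, serotonin transporter and dopamine transporter activity in only a selected number of ROIs". Its ROI list ends "as well as the caudate, putamen, thalami, midbrain, hypothalamus, cerebellum, and cingulate gyrus regions". The normalisation rule follows: "Counts will be obtained for each ROI and normalized to the mean whole brain counts". The quantity tested is then given: "ratios of activity in each ROI will be compared across scans for each neuropsychological state".

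The remaining text of section 9 names no cerebellar denominator. The voxel-wise (SPM) part of 9.1 allows global or reference-region activity as a nuisance term, without naming the region. Sections 9.2 to 9.7 name no reference region.

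**The concern.** An analyst working from 4.2(b) and one working from 9.1 would compare different quantities before and after the retreat, and each could claim to be following the plan. Three things are at stake.

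- **Interpretation.** The protocol justifies the cerebellar ratio as a measure related to binding. It gives no such justification for the whole-brain ratio. If the whole-brain mean includes the regions where binding changes, a true change enters both numerator and denominator.
- **Choice of denominator.** Section 9.3 applies p < 0.05 to every measure, and no multiplicity correction is stated for the 19 ROIs listed in 9.1. With two denominators available and neither tied to the primary comparison in section 9, the choice could be made after the results are seen.
- **Reporting.** Section 9.6 promises to report deviations from the statistical plan. As written, analysing the declared primary outcome departs from 9.1, and following 9.1 departs from 4.2(b).

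**Working it through.** **Step 1: the texts side by side.**

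| Item | Section 4.2(b) | Section 9.1, ROI paragraph |
|---|---|---|
| Scope | SERT and DAT | Blood flow, SERT and DAT |
| Denominator | Cerebellum | Whole-brain mean |
| Status | Declared primary outcome | Ratio compared across scans; not called primary |
| Whole brain | Part above the basal ganglia, used to confirm | Not defined |

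Could the 9.1 rule be meant for blood flow alone? Nothing in the paragraph limits it in that way: it names both transporters and describes co-registering the SPECT images. Blood flow in this study is an fMRI measure. Section 2.2 says "We have chosen fMRI imaging of cerebral blood flow for several reasons", and the second objective in section 3 concerns "changes in cerebral blood flow using fMRI". A blood-flow-only reading is therefore not the natural one.

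Does other text reconcile the two? The confirming values in 4.2(b) mean that both references will be measured, but that text does not put the cerebellar ratio into the 9.1 comparison. The SPM nuisance term belongs to a voxel-wise model and is not an ROI comparison.

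**Step 2: how far the two ratios can differ.** The plan gives no figure for this, so there is none to reproduce. Inputs:

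- Change of 10% and SD of 15%, from section 9.2, which does not say which denominator they refer to.
- f, the share of baseline whole-brain counts held by the regions that change. This is an assumption; the documents do not give it.
- Cerebellar counts unchanged. This is also an assumption.

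Formulas:

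- Change in ROI/cerebellum = 1.10/1 − 1 = 10% for every f.
- Change in ROI/whole brain = 1.10/(1 + 0.10f) − 1.
- Apparent change in a region that did not change, including the cerebellum = 1/(1 + 0.10f) − 1.
- SD at which the whole-brain ratio has the same power as the cerebellar ratio with an SD of 15% = 15% × (whole-brain change)/10%. This holds for any t-test at a fixed sample size, because power depends on effect/SD.

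| f | ROI/cerebellum | ROI/whole brain | Unchanged region | Equal-power SD |
|---|---|---|---|---|
| 0 | 10.00% | 10.00% | 0% | 15.00% |
| 0.01 | 10.00% | 9.89% | −0.10% | 14.84% |
| 0.05 | 10.00% | 9.45% | −0.50% | 14.18% |
| 0.2 | 10.00% | 7.84% | −1.96% | 11.76% |
| 0.5 | 10.00% | 4.76% | −4.76% | 7.14% |

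The row f = 0 applies if the denominator excludes the changing regions, as it would for a change confined to midbrain or basal ganglia when whole brain means the part above the basal ganglia. Rows up to 0.05 illustrate a focal change; 0.2 and 0.5 illustrate a widespread one.

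**Step 3: can the declared outcome be recovered?** Yes. Within one scan, (ROI/whole brain) ÷ (cerebellum/whole brain) = ROI/cerebellum, whatever f is. This must be done scan by scan for each subject, and 9.1 does not ask for it.

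**The case against.** The strongest reply is that this is one combined document, that 4.2(b) alone declares a primary outcome, and that 9.1 never calls its ratio primary. On that view 9.1 is a general ROI procedure for several modalities and lacks only a cross-reference. There is some support. The 9.1 ROI list is mostly cortical, whereas the 4.2(b) list is subcortical plus cerebellum, and the SPM text speaks only of blood-flow differences. The study is also labelled exploratory in 9.2, both sets of values are collected, and the distortion is small for a focal change.

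Much of this stands, and it rules out several stronger readings that a reader might infer:

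- **That the primary outcome has been abandoned or is lost.** It is declared in 4.2(b), and it can be computed from the collected data.
- **That listing the cerebellum as an ROI in 9.1 shows it is not the reference.** Section 4.2(b) also lists it among its ROIs and then uses it as the reference, so the listing shows nothing either way.
- **That power is lost.** The whole-brain ratio shows a smaller change, but its SD may also differ, and the documents give no SD by denominator.
- **That the cerebellum should not be tested as a SPECT ROI.** Under the whole-brain analysis, its pre/post comparison is a useful check that the reference is stable.

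The reply does not remove the conflict. The 9.1 paragraph names SERT and DAT, gives one denominator without exception, and says that the resulting ratios are what is compared. This is a stated rule that differs from the outcome definition, which goes beyond a missing detail.

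**Conclusion.** The concern holds as a conflict between two stated rules. Confidence is high on the wording and low on the size of any effect. With a focal 10% change, an unchanged cerebellum and f between 0 and 0.05, the understatement is 0 to about 0.5 percentage points, and it grows if the change is widespread. The value of f is assumed throughout, and the direction of any effect on power is not determined. The point should be fixed because it concerns the primary outcome and leaves the denominator open at an uncorrected 0.05 level. It does not put the data or the feasibility of the study at risk.

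**What to change.** In the ROI paragraph of 9.1:

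1. State that SERT and DAT counts in each target ROI are divided by cerebellar counts from the same scan, as in 4.2(b), and that this ratio is the primary quantity compared pre/post.
2. Keep the whole-brain-normalised ratio as a sensitivity analysis. Define whole brain, and say whether it is the region above the basal ganglia mentioned in 4.2(b).

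The cerebellum may stay in the ROI list as a check on reference stability under the whole-brain analysis. Two additions are optional: a sentence on normalisation of the fMRI blood-flow data, and naming the SPM nuisance term for the SPECT data.

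The cost is two to four sentences. Both sets of values are already to be obtained under 4.2(b), so no new scans or data are needed.
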